LDL and blood biomarkers as mediators for plaque progression: In the event that both statin effects on NCP progression and biomarker changes are apparent, the association between changes in LDL and these biomarkers and NCP progression will be examined using graphical techniques and normal errors and logistic regression (for the subpopulations with and without NCP at entry respectively. A mediating effect of these biological factors will be evaluated by examination of changes in the estimated statin effect on NCP upon adjustment for these biological factors. Those biomarkers with the strongest mediating effect on plaque progression will be measured in the entire REPRIEVE (A5332) cohort to determine their association with MACE.

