Next, we will conduct a mediation analysis to test whether pitavastatin lowers the incidence of  $\geq 30\%$  eGFR decline by reductions in biomarkers assessed. To address mediation that pitavastatin will reduce the incidence of eGFR decline through improvements in systemic and vascular inflammation and oxidative stress, we will apply the regression technique described by Judd and Kenny and elaborated by MacKinnon [Judd 1981; MacKinnon 1994]. The technique, will account for each biomarker separately and for all biomarkers simultaneously (mediators) using two regression equations ([Table 2](#)). Y is the outcome result (eg, eGFR decline  $\geq 30\%$ ),  $X_p$  is randomization to pitavastatin versus placebo and  $X_i$  represents the k biomarkers, our purported mediators. The total effect of pitavastatin on the outcome (measured by the coefficient,  $\tau$ ) is the sum of direct effect ( $\tau'$ ) of treatment and the mediated, or indirect, effects. The assessment of the amount of change in these biomarkers mediating the effect of pitavastatin on eGFR decline will be addressed by considering two multivariable regression models (see [Table 2](#)). First, a regression model that estimates the decreased risk of a  $\geq 30\%$  eGFR decline with pitavastatin without mediating risk factors but considering other risk factors (eg, age, race, sex, hypertension) and a second Cox regression model that further makes adjustment for the mediating risk factor (ie, biomarkers of inflammation and oxidative stress). For these analyses, the parameter of interest (ie, log hazard ratio) is not the impact of pitavastatin on outcomes, but rather the difference in the estimated impact of pitavastatin

between the two models ( $\tau' - \tau$ ), which serves as a direct measure of the degree to which the effect of pitavastatin is due to improvements in these biomarkers. Whether the biomarkers "significantly" mediate the benefits of pitavastatin can be addressed by creating empirical confidence intervals around the change in its coefficient. Confidence interval of the change in the coefficient associated with the disparity will be calculated using bootstrap methods.

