## 2 Objectives and Estimands

### 2.1 Primary Objective

To determine the effects of pitavastatin on the morphology and composition of coronary atherosclerotic plaque, (including the progression of noncalcified plaque (NCP) volume), and whether these effects are modulated by markers of inflammation and immune activation.

Primary Estimand	
Estimand description	An estimand defines the target of estimation for a particular trial objective (i.e. “what is to be estimated”). This combines all the estimand elements outlined below into a single, succinct sentence.
Treatment	Treatment groups
Pitavastatin 4mg per day	Pitavastatin 4mg per day or placebo
Target population	Analysis set
PWH on stable ART with low to moderate cardiovascular risk and no known current indication for statin treatment.	All randomized participants with a REPRIEVE (A5332) entry visit. Participants who were consented but never returned to the clinic for their REPRIEVE (A5332) entry visit (regardless of whether the participant was formally randomized) will be considered inadvertent enrollments and excluded.
Variable(s)	Outcome measure(s)
Change in noncalcified plaque volume (NCP)  Change in volume of plaque and calcified plaque will be examined as secondary variables.	See Section 3 for more detailed outcome descriptions • Absolute change in NCP volume from entry to year 2. • NCP progression defined as any increase (>0) in NCP volume or incident NCP for those without NCP at entry (based on qualitative read) For sensitivity analyses, • Qualitative assessment of at least one segment with NCP on the 2 year CT. • Quantitative NCP volume at 2 year CT
Handling of intercurrent events	Handling of missing data

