## 3.4 Markers of Immune Function

Levels at entry, 4 months and 2 years, and changes from study entry to 4 months and 2 years (unless stated otherwise).

- Soluble markers of monocyte activation
  - sCD163, sCD14, MCP-1
- Monocyte populations (entry and 2 years only)
  - %CD14+CD16+ (inflammatory/intermediate) monocytes
    - Classical and non-classical subsets presented descriptively
- Markers of T-cell activation and T-cell exhaustion (entry and Year 2 only)
  - CD38+DR+ on CD4+ and CD8+
- Markers of inflammation:
  - Lp-PLA2, hsCRP, IL6, hs troponin, oxLDL
- Markers of coagulation
  - D-Dimer

Future analyses will interrogate the broader spectrum of immune phenotyping that has been performed on collected PBMCs.

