### 7.5 LDL and blood biomarkers as mediators for plaque progression

In the event that both statin effects on NCP progression and biomarker changes are apparent, the association between changes in LDL and these biomarkers and NCP progression will be examined using graphical techniques and normal errors and logistic regression (for the subpopulations with and without NCP at entry respectively. A mediating effect of these biological factors will be evaluated by examination of changes in the estimated statin effect on NCP upon adjustment for these biological factors.

Since the hypothesized mechanism is that sustained high levels of immune activation and inflammation precede and contribute to progression of NCP volume and high risk plaque features, these analyses will relate short term changes in these biomarkers (over 4 months) to longer term changes in NCP volume and morphology after two years.

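### SAP 7.5 judges mediation from the change in the estimated statin effect after adjustment but attaches no measure of uncertainty to that change, although protocol Appendix V plans a bootstrap interval for the same quantity

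*SAP*

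**What the plan says.** The substudy's primary objective (SAP 2.1) covers the statin effect on plaque and "whether these effects are modulated by markers of inflammation and immune activation". SAP 7.5 is the only part of the SAP's analysis plan that links blood markers to the statin effect on noncalcified plaque (NCP).

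- **Entry condition.** The analysis is run "In the event that both statin effects on NCP progression and biomarker changes are apparent". The SAP does not define when an effect is apparent, or say whether this is judged once or marker by marker.
- **Association step.** The relation of changes in LDL and the biomarkers to NCP progression is examined by graphs, by normal-errors regression in participants with NCP at entry, and by logistic regression in those without.
- **Mediation step.** "A mediating effect of these biological factors will be evaluated by examination of changes in the estimated statin effect on NCP upon adjustment".
- **Timing.** "these analyses will relate short term changes in these biomarkers (over 4 months") to plaque change at two years. With LDL, the month-4 candidates in SAP 3.4 are "sCD163, sCD14, MCP-1" and "Lp-PLA2, hsCRP, IL6, hs troponin, oxLDL", nine in all. Protocol Appendix II excludes D-dimer at month 4; SAP 3.4 does not repeat that exclusion.

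The 95% intervals and 5% error rate in SAP 7.1 apply to treatment-group comparisons, not to the change in a coefficient.

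Protocol Appendix II, section 9.5.2, uses the same wording and adds: "Those biomarkers with the strongest mediating effect on plaque progression will be measured in the entire REPRIEVE (A5332) cohort", in order to study their association with MACE. SAP 7.5 does not carry that sentence over, and the SAP version history does not list its removal.

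Protocol Appendix V, Objective 3, takes as its parameter the difference between the pitavastatin coefficients with and without the biomarkers. It then states: "Confidence interval of the change in the coefficient associated with the disparity will be calculated using bootstrap methods".

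**The concern.** The change in a treatment coefficient when a marker is added is an estimate with sampling error. Under no mediation it is centred on zero, and its standard error is proportional to the statin's effect on the marker. A marker that the statin moves strongly can therefore show a sizeable change by chance, while a weakly moved marker cannot. Read without an interval, the size of the change partly reflects how far the statin moves the marker, whether or not the marker affects plaque.

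This bears on the comparison the substudy was built to make. A secondary objective (SAP 2.2) asks for the relative contributions of immune activation and of traditional factors including LDL. Protocol Appendix II, section 2.2, says the answer would point either to further LDL lowering or to immune-directed strategies. Protocol section 2.1.3.4 reports a 31.1% fall in LDL with pitavastatin 4 mg over 12 weeks in people with HIV. LDL is thus a plausible strongly moved marker, although the documents give no SD with which to express that fall as a standardized shift.

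**Working it through.** The documents give no error rate for the mediation step, so there is no planned figure to reproduce.

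**Inputs from SAP Appendix I.** Total 800; 50% with NCP at entry; 15% not evaluable; equal allocation; SD of percent change 20%; detectable difference 6 points (the planning table shows 12% vs 5%, i.e. 7 points).

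Participants per arm with NCP at entry: 800 × 0.50 × 0.85 / 2 = 170.

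As a check on that n, the two-sided 5% power is 79% for 6 points and 89.7% for 7 points. The gap from the stated 90% at 6 points is a separate matter and does not affect what follows.

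**Assumed, not in the documents.** Statin shift in the marker, d, in within-arm SD units; apparent read as p<0.05 for the statin effect on NCP; no within-arm relation between marker and NCP (no true mediation).

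**Formula.** In the linear model, let τ be the statin coefficient without the marker and τ' the coefficient with it. Then τ − τ' = a × b, where a is the statin effect on the marker and b the marker's effect on NCP given arm. With b = 0, the estimate is centred on zero with

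SE(τ − τ') ≈ d × 20/√340 = d × 1.085 points.

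The sign is a coin toss. Ten percent of a 6-point effect is 0.6 points, so the chance of apparent mediation above 10% is about 1 − Φ(0.6/SE). The simulation used 4,000 datasets per scenario, 170 per arm and nine markers with pairwise correlation 0, 0.3 or 0.5. Its results are conditional on a significant statin effect on NCP.

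| Shift d | SE (points) | 0.6/SE | Normal approximation | Simulated, above 10% | Simulated, above 20% |
|---|---|---|---|---|---|
| 0.3 SD | 0.325 | 1.84 | 3.3% | 3-4% | 0.1-0.3% |
| 0.5 SD | 0.542 | 1.11 | 13.4% | 11-13% | 1.5-1.7% |
| 1.0 SD | 1.085 | 0.55 | 29.0% | 26-28% | 12-13% |
| 1.5 SD | 1.627 | 0.37 | 35.6% | 34-36% | 21-22% |

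In the same runs any shrinkage at all occurred in 49-53%. The simulated values tend to sit slightly below the approximation because requiring significance selects larger estimated effects, which raises the 10% bar.

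**Sensitivity to the effect size.** With 7 points, 0.7/SE gives 1.6%, 9.8%, 25.9% and 33.4%.

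**Sensitivity to the outcome.** SAP 3.2.1 makes absolute change primary and percent change supportive. The planning table for those with plaque at entry gives 30 (SD 68) vs 12 (SD 64) mm³: difference 18, pooled SD √((68² + 64²)/2) = 66.0. Then SE = d × 66.0/√340 = d × 3.58, and the chance of exceeding 1.8 mm³ is 4.7%, 15.7%, 30.8% and 36.9%. This ignores any precision gained from adjusting for baseline volume.

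**What a test on the change would do.** As a stand-in for an interval, the simulation required both paths (statin to marker, and marker to NCP) to be significant at two-sided 5%. False attenuation then fell to about 2-3% per marker for every d of 0.3 or more. The logistic half of SAP 7.5 was not simulated.

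**The case against.** The strongest reply is that SAP 7.5 describes an evaluation, not a decision rule. It does not say that any shrinkage counts, or that a marker will be declared a mediator. That stands. A reader might infer that each non-mediating marker will be called a mediator half the time, and that among several markers one will almost always be found (for k independent markers, 1 − 0.5^k: 87.5% for three, 99.8% for nine). The documents do not support this: those rates require a rule that any shrinkage counts, and the family-wise figures also assume independent markers. With nine markers at d = 0.3 and correlation 0.5, the chance of at least one shrinking is 90%. If the statin moves no marker and the entry condition is applied marker by marker at 5%, it is 17-20%.

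Second, the sentence before the mediation step examines marker-NCP association by regression, which bears on exactly the case checked here. This stands in part. The text does not say whether that regression adjusts for arm, and does not tie its result to the mediation conclusion.

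Third, the sentence on strongest mediators is in the protocol only. It selects assays for further study against MACE, so a false lead costs an assay and is not a published claim. That stands. The ranking still rests on estimates whose noise differs by marker.

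Fourth, protocol section 9.6.1 promises conservative interpretation across the clinical and mechanistic hypotheses, weighing degree of significance and consistency. That is a real commitment, but degree of significance cannot be weighed for a quantity that has no standard error.

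Finally, at shifts of 0.3 SD chance mediation above 10% is uncommon, and LDL is not named in the primary objective's clause on modulation. Both are correct. The problem is concentrated in strongly moved markers and in the secondary objective on relative contributions.

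**Conclusion.** The concern holds as a gap in method: the quantity on which mediation is judged has no interval or test in SAP 7.5 or in protocol Appendix II, while the same protocol plans one for the same kind of quantity in Appendix V. For a marker with no effect on plaque, apparent mediation above 10% is a minor risk at small shifts (about 3-4% at 0.3 SD) and a substantial one at large shifts (about 35% at 1.5 SD).

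These figures rest on the planning n and SD, on the linear model in participants with NCP at entry, and on assumed marker shifts. The 10% mark is a yardstick for size, not a threshold in the SAP. The documents do not support the stronger inference that the plan will declare false mediators half the time or almost always, and it forms no part of this conclusion. The change should be made, because it costs little and the method is already in the protocol.

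**What to change.** In SAP 7.5:

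- For participants with NCP at entry (linear model), report τ − τ' for each marker with a bootstrap 95% confidence interval, following Appendix V, Objective 3.
- For participants without NCP at entry (logistic model), compute the change on the risk-difference scale or another collapsible scale, also with a bootstrap interval. A change in log odds ratio can arise from adjustment alone, and an interval does not cure that. Appendix V is a precedent for the interval, not for the scale.
- Use these intervals, and not the rank of the point estimates alone, when choosing biomarkers for the full cohort under protocol Appendix II, section 9.5.2.

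It would also help to state what counts as an apparent effect and to list the month-4 markers that enter. A formal multiplicity-adjusted rule for declaring mediators is optional.

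The cost is a few sentences and a bootstrap loop on data already collected. The downside is that fewer markers will be described as mediators.

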## Appendix I Sample Size Considerations

[Copied Verbatim from the REPRIEVE A5333S Protocol, Version 5.0, Section 9.2.]

The target sample size for the Mechanistic Substudy of REPRIEVE (A5333s) is 800 participants that will be approximately equally distributed between the study arms.

This sample size was determined to have high power to detect clinically relevant differences between the two study groups both with respect to plaque progression (among those with plaque at study entry) and rates of incident plaque (among those plaque-free at entry). Specifically, the total sample size of 800 subjects will provide 90% power to detect a 6% difference between the study groups in the percent change in NCP volume over 2 years among those with plaque at entry and 90% power to detect 13 percentage point difference in the probability of plaque development over 2 years. These effect sizes translate to a combined estimated 14 percentage point difference in the probability of NCP progression over two years and are based on the following assumptions:

50% of study participants will have evidence of NCP at study entry [Lo 2010]

A SD of 20% for the percent change over 2 years among participants with evidence of plaque at entry

An annual rate of incident plaque development of 12% among participants without plaque at entry

15% of participants entering the substudy will not be evaluable for study entry or 2 year NCP volume.

Together, the effects of statins acting in these two groups (those with and without evidence of NCP at study entry) will provide for a 7% lower prevalence of NCP after 2-years of statin treatment. Expectations for NCP prevalence and progression both as a whole and according to whether NCP was present at study entry are illustrated in the table below. These estimates are based on a simulation that further assumed the following:

Average volume NCP 250mm^3 (SD=200) among participants with NCP at entry.

Average volume NCP 40mm^3 (SD=20) at 2 years among participants without NCP at entry without statin treatment.

Average volume NCP 20mm^3 (SD=20) at 2 years among participants without NCP at entry with statin treatment.

NCP distributions were also assumed to follow a gamma distribution with size and shape parameters determine to provide the desire mean and standard deviations.

Table 9.2-1: Cells constituting the primary targeted group comparisons are shown in bold.

		At study entry			At two 2 years						
		NCP (%)	NCP volume (mm  )		NCP (%)	NCP volume (mm  )		Change in NCP volume (mm  )		Percent change in NCP volume (%) 	
			Mean (SD)	[P5, P95]		Mean (SD)	[P5, P95]	Mean (SD)	[P5, P95]	Mean (SD)	[P5, P95]
Control	Overall 	50%	121 (186)	[0, 509]	59%	140 (210)	[0, 573]	19 (51)	[-21, 103]	17% (33%)	[-10%, 100%]
	No plaque at entry	-	-	21%	9 (19)	[0, 51]	9 (19)	[0, 51]	21% (41%)	[0%, 100%]	
	No plaque at 2 years				-	-	-	-	-	-	
	Plaque at 2 years				40 (20)	[17, 79]	40 (20)	[17, 79]	100% (0%)	[100%, 100%]	
	Plaque at entry	251 (198)	[26, 637]		281 (231)	[28, 730]	30 (68)	[-38, 153]	12% (20%)	[-14%, 49%]	
Statin	Overall 	50%	120 (185)	[0, 507]	52%	127 (198)	[0, 536]	7 (45)	[-42, 76]	7% (24%)	[-17%, 60%]
	No plaque at entry	-	-	8%	2 (8)	[0, 14]	2 (8)	[0, 14]	8% (27%)	[0%, 100%]	
	No plaque at 2 years				-	-	-	-	-	-	
	Plaque at 2 years				23 (19)	[2,60]	23 (19)	[2,60]	100% (0%)	[100%, 100%]	
	Plaque at entry	250 (197)	[26, 633]		262 (216)	[26, 682]	12 (64)	[-66, 123]	5% (20%)	[-21%, 43%]	

 In estimation of overall means, participants without evidence of NCP are assigned a value of 0 for volume and change.

 In estimation of percentage change, participants without evidence of NCP at study entry with NCP at 2 years are assigned a value of 100%.

These desired statin effects on NCP volume are similar to those seen in intravascular ultrasound (IVUS) studies [Nissen 2006; Nicholls 2005]. Although no data exist to directly inform the clinical relevance of these differences, randomized comparisons of high vs. low dose statin therapy among non-HIV-infected patients have demonstrated favorable effects on atherosclerotic plaque of a similar magnitude as well as on adverse cardiac events, among non-HIV patients [Nissen 2006]. Further, data from the "Coronary CT Angiography Evaluation for Clinical Outcomes (CONFIRM) registry suggest that the presence of non-obstructive CAD is predictive major adverse cardiac events independent of traditional risk factors, degree of stenosis and coronary artery calcification (HR 2-5) [Hulten 2013]. The proposed mechanistic study will further add to this body of evidence investigating, for the first time in HIV-infected population, the association of NCP (both the presence and magnitude) as well as changes in volume relate to events. For this exploratory analysis, a larger sample size will be beneficial, in order to accrue CVD events to relate to plaque morphology.

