Failure to start statin : Included per randomized treatment (treatment policy) Change in statin strategy : Included per randomized treatment (treatment policy) Includes discontinuation or change of statin Evidence of critical stenosis at treatment start : Included per randomized strategy (treatment strategy) Interval stent placement or bypass *: Included per randomized strategy (treatment policy strategy) Death prior to Year 2 scan : Treated as missing data (hypothetical policy)	Missing data due to missed visits or unreadable scans will be assumed missing completely at random and ignored i.e., the primary analysis will be a complete case analysis including participants with pair baseline and year 2 scans. Sensitivity analyses will include multiple imputation for missing data.
Population-level summary measure	Analysis approach
Mean change NCP volume over 2 years	Linear regression (normal errors assumption). In the event of extreme violation of normality, outcomes will be log transformed (giving a percentage change interpretation of the treatment effect). Modeling will adjust for CD4 and sex (stratification factors), and for baseline NCP volume.

\* Stented or bypassed coronary artery segments are not considered on the entry and year 2 scan as part of the read protocol for plaque volume.

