##### 3.2.1 Change NCP volume over 2 years (Primary)

- Continuous outcome:
  - Absolute change: NCP volume at 2 years – NCP volume at entry
  - Percentage change: (NCP volume at 2 years – NCP volume at entry) / NCP volume at entry (Supportive)
- Based on quantitative read whenever available (including for participants with no evidence of NCP based on the corresponding qualitative read).
  - Participants without a quantitative read and no evidence of NCP based on the corresponding qualitative read will be assigned a value of zero for both absolute and percentage change.

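### The A5333s sample-size text claims 90% power for a 6% difference in percent change of NCP volume; its own inputs give 79% for 6 points and 90% for 7 points

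*SAP*

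**What the plan says.** Protocol Appendix II, section 9.2, and SAP Appendix I (headed "Copied Verbatim from the REPRIEVE A5333S Protocol, Version 5.0, Section 9.2") make two power claims in one sentence. The first is that "the total sample size of 800 subjects will provide 90% power to detect a 6% difference between the study groups" in percent change of NCP volume over two years, among those with plaque at entry. The second is "90% power to detect 13 percentage point difference in the probability of plaque development over 2 years" among those without plaque at entry.

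The assumptions follow directly. Half of participants have NCP at entry, "A SD of 20% for the percent change over 2 years among participants with evidence of plaque at entry" is assumed, and "15% of participants entering the substudy will not be evaluable for study entry or 2 year NCP volume". Arms are about equal in size.

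Table 9.2-1 comes next, with the caption "Cells constituting the primary targeted group comparisons are shown in bold". For participants with plaque at entry, the SAP's copy sets in bold a mean percent change of 12% (SD 20%) for control and 5% (SD 20%) for statin.

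**The concern.** The sentence puts the design difference at 6, while the table it introduces shows 12% against 5%, a difference of 7. Both cannot be the effect that 800 participants detect with 90% power. If the sentence is wrong, the published plan understates the smallest true difference the design detects with 90% power. A reader would then take the chance of missing a true 6-point effect to be 10%. This is the only power statement the documents give for change in NCP volume.

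**Working it through.** **Inputs.** From the sample-size section: 800 enrolled, 1:1, 50% with NCP at entry, 15% not evaluable, SD 20 percentage points. Testing is two-sided at 5% (Protocol 9.6.1; SAP 7.1 gives a 5% error rate and two-sided 95% intervals).

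**Analysable participants per arm with NCP at entry:** 800 × 0.85 × 0.50 / 2 = 170. The number without NCP at entry is the same.

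**Plan's own figure, incident plaque.** At 170 per arm, the table's 21% against 8% gives 92.9% power. Compounding 12% a year instead gives 22.6%, and 22.6% against 9.6% gives 90.7%. Either way the claim of 90% for 13 points holds at 170 per arm, so this is the sample size the sentence was built on.

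**Percent change.** Normal approximation:

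- SE = 20 × √(2/170) = 2.169
- Power = Φ(difference / SE − 1.960)
- 6 points: 6 / 2.169 = 2.766; Φ(0.806) = **79.0%** (78.8% from the noncentral t; 78.9% in a 40,000-trial simulation)
- 7 points: **89.7%** (89.6% from the noncentral t; 89.5% in simulation)
- Detectable with 90% power: (1.960 + 1.282) × 2.169 = **7.03 points**

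**What 90% at 6 points would need.** n per arm = 2 × (20 × 3.242 / 6)² = 233.5, so 234. That is 468 / (0.50 × 0.85), or about 1,102 enrolled. Alternatives are an SD of about 17.1, or about 69% with NCP at entry.

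**Could rounding in the table hide a 6-point target?** The percent cells alone would allow 11.5 − 5.5 = 6.0. The mm³ columns narrow this:

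- 30/251 − 12/250 = 12.0% − 4.8% = 7.15 points
- Lowest: 29.5/251.5 − 12.5/249.5 = 6.72 points, power 87%
- Highest: 30.5/250.5 − 11.5/250.5 = 7.58 points, power 94%

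This step treats percent change as independent of baseline volume, which the table supports. Independence predicts an SD of change of √[(251² + 198²)(0.12² + 0.20²) − (251 × 0.12)²] = 68.2 for control and, likewise, 64.4 for statin. The table prints 68 and 64.

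**Other ways to reach 90% at 6 points:**

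| Variant | Power |
|---|---|
| No losses (200 per arm), two-sided | 85.1% |
| 15% loss, one-sided 5% | 86.9% |
| Loss taken as 800/1.15 (174 per arm), two-sided | 79.9% |
| All 680 evaluable participants, two-sided | 97.5% |
| No losses and one-sided 5% | 91.2% |
| True difference 6.49 (rounds to 6), 170 per arm, two-sided | 84.9% |

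Only the one-sided, no-loss variant comes close to 90%. It contradicts both the two-sided testing and the listed 15% loss.

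**The case against.** The strongest counter-argument concerns the unit. The sentence gives plain per cent for NCP volume but percentage points for incident plaque, so the 6% might be a relative difference in follow-up volume. The table's scenario gives 1 − 1.05/1.12 = 6.25% on that scale. A simulation with gamma-distributed follow-up ratios (means 1.12 and 1.05, SD 0.20) gave about 90% power on the raw scale and 91% on the log scale. On that reading, 6% at 90% roughly describes the table's own scenario.

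This may be how the figure arose, but it is not what the sentence says. The sentence names a difference in percent change, and the SD of 20% is on that scale. The same section calls the 59% to 52% gap in NCP prevalence 7% lower, so it uses plain per cent for points elsewhere. An exact 6% relative difference is 1.12 × 6% = 6.72 points, with 87% power.

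Baseline adjustment is a second possible escape, since the SAP states that "Modeling will adjust for CD4 and sex (stratification factors), and for baseline NCP volume". To reach 90% at 6 points it would have to remove about 27% of the variance of percent change, because 1 − (17.07/20)² = 0.27. Neither document gives such a correlation, and the test in the protocol is a stratified t-test.

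The arguments on impact do stand. Accrual closed in February 2018, the appendix reprints planning text, percent change is supportive in SAP 3.2.1 with absolute change primary, and a reader who relies on the table is not misled. They limit the consequences but do not make the stated figure right. The 90.7% for incident plaque also depends on annual compounding; the table's 21% is nearer 1 − exp(−0.24) = 21.3%, so 92.9% is the better check. Both exceed 90%.

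**Conclusion.** The point holds. On the section's own inputs and two-sided 5% testing, the design has 79% power for 6 percentage points and 89.7% for 7. The text therefore understates the 90% detectable difference by one point, and the miss rate for a true 6-point effect is 21% rather than 10%. This rests on 170 analysable participants per arm and on reading the 6% on the percent-change scale, where the SD is defined. The error is confined to this one figure, which appears in both documents. The sample size fits the 7-point difference in Table 9.2-1, the incident-plaque statement stands, and no analysis is affected.

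**What to change.** In Protocol Appendix II, section 9.2, state 90% power for a difference of 7 percentage points (12% against 5%, as in Table 9.2-1), or keep 6 points and state 79%. Give the unit as percentage points. In the SAP, leave the reprinted text as it is and add a correcting note beneath Appendix I, because it is presented as a verbatim copy.

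The cost is one figure and one note. Sample size and analyses do not change; the difference stated at 90% power becomes 7 points instead of 6.

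Optionally, since absolute change is the primary outcome in the SAP, the note could add approximate unadjusted power derived from Table 9.2-1:

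- All paired participants, 12 mm³: SE = √[(51² + 45²)/340] = 3.69; power about 90%.
- NCP at entry, 18 mm³: SE = √[(68² + 64²)/170] = 7.16; power about 71%.

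Adjusting for baseline volume would raise these to about 92–93% and 74%. Those adjusted values use correlations inferred from the table's rounded SDs and should be labelled as such. The correction does not depend on any of these additions.
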